6.4 Recording of Adverse Events

At each contact with the subject, the study team must seek information on adverse events by specific questioning and, as appropriate, by examination. Information on all adverse events should be recorded immediately in the source document, and also in the Adverse Event Case Report Form (CRF). All clearly related signs, symptoms, and abnormal diagnostic, laboratory or procedure results should be recorded in the source document.

All adverse events occurring during the study period must be recorded. The clinical course of each event should be followed until resolution, stabilization, or until it has been ultimately determined that the study treatment or participation is not the probable cause. Serious adverse events that are still ongoing at the end of the study period must be followed up, to determine the final outcome. Any serious adverse event that occurs after the study period and is considered to be at least possibly related to the study treatment or study participation should be recorded and reported immediately.

6.5 Reporting of Serious Adverse Events and Unanticipated Problems

The sponsor-investigator is responsible to evaluate all adverse events to determine reporting requirements to the IRB and FDA. When an adverse event has been identified, the study team will take appropriate action necessary to protect the study participant and then complete the Study Adverse Event Worksheet and log. The sponsor-investigator will evaluate the event and determine the necessary follow-up and reporting required. The reporting will need to occur within two working days.

6.6 Sponsor-Investigator Reporting: Notifying the Mayo IRB

The sponsor-investigator will report to the Mayo IRB any UPIRTSOs and Non-UPIRTSOs according to the Mayo IRB Policy and Procedures.

Any serious adverse event (SAE) which the Principal Investigator has determined to be a UPIRTSO must be reported to the Mayo IRB as soon as possible but no later than five working days after the investigator first learns of the problem/event.

Information collected on the adverse event worksheet (*and entered in the research database*):

- Subject's Name
- Medical record number:
- Disease/histology (if applicable):
- The date the adverse event occurred:
- Description of the adverse event:
- Relationship of the adverse event to the research (drug, procedure, or intervention):
- If the adverse event was expected:
- The severity of the adverse event: (use a table to define severity scale 1-5)
- If any intervention was necessary:
- Resolution: (was the incident resolved spontaneously, or after discontinuing treatment)
- Date of Resolution:

The sponsor-investigator will review all adverse event reports to determine if specific reports need to be made to the IRB and FDA. The sponsor-investigator will sign and date the adverse event report when it is reviewed. For this protocol, only directly related SAEs/UPIRTSOs will be reported to the IRB.

6.7 Sponsor-Investigator Reporting: Notifying the FDA

The sponsor-investigator will report to the FDA all unexpected, serious suspected adverse reactions according to the required IND Safety Reporting timelines, formats and requirements.

Unexpected fatal or life threatening suspected adverse reactions where there is evidence to suggest a causal relationship between the study drug/placebo and the adverse event, will be reported as a serious suspected adverse reaction. This will be reported to the FDA on FDA Form 3500A, no later than 7 calendar days after the sponsor-investigator's initial receipt of the information about the event.

Other unexpected serious suspected adverse reactions where there is evidence to suggest a causal relationship between the study drug/placebo and the adverse event, will be

reported as a serious suspected adverse reaction. This will be reported to the FDA on FDA Form 3500A, no later than 15 calendar days after the sponsor-investigator's initial receipt of the information about the event.

Any clinically important increase in the rate of serious suspected adverse reactions over those listed in the protocol or product insert will be reported as a serious suspected adverse reaction. This will be reported to the FDA on FDA Form 3500A no later than 15 calendar days after the sponsor-investigator's initial receipt of the information about the event.

Findings from other studies in human or animals that suggest a significant risk in humans exposed to the drug will be reported. This will be reported to the FDA on FDA Form 3500A, no later than 15 calendar days after the sponsor-investigators initial receipt of the information about the event.

For this multi-center clinical trial, in addition to reporting certain unanticipated problems and adverse events noted above to the FDA, it is the responsibility of the study sponsor to report those same adverse events or findings to participating investigators.

CONFIDENTIAL

This material is the property of the Mayo Clinic. Do not disclose or use except as authorized.

FDA Definitions (21 CFR 312.32(a))

- A. **Adverse Event:** any untoward medical occurrence associated with the use of a drug in humans, whether or not considered drug related.
- B. **Suspected Adverse Reaction:** any adverse event for which there is a reasonable possibility that the drug caused the adverse event. For the purposes of IND safety reporting, ‘reasonable possibility’ means there is evidence to suggest a causal relationship between the drug and the adverse event. A suspected adverse reaction implies a lesser degree of certainty about causality than adverse reaction, which means any adverse event caused by a drug.
- C. **Adverse Reaction:** any adverse event caused by a drug. Adverse reactions are a subset of all suspected adverse reactions where there is reason to conclude that the drug caused the event.
- D. **Unexpected:** An adverse event or suspected adverse reaction is considered “unexpected” if it is not listed in the investigator brochure or is not listed at the specificity or severity that has been observed; or, if an investigator brochure is not required or available, is not consistent with the risk information described in the general investigational plan or elsewhere in the current application, as amended. For example, under this definition, hepatic necrosis would be unexpected (by virtue of greater severity) if the investigator brochure referred only to elevated hepatic enzymes or hepatitis.
- E. **Serious:** An adverse event or suspected adverse reaction is considered “serious” if, in the view of either the investigator or sponsor, it results in any of the following outcomes: Death, a life-threatening adverse event, inpatient hospitalization or prolongation of existing hospitalization, a persistent or significant incapacity or substantial disruption of the ability to conduct normal life functions, or a congenital anomaly/birth defect. Important medical events that may not result in death, be life-threatening, or require hospitalization may be considered serious when, based upon appropriate medical judgment, they may jeopardize the patient or subject and may require medical or surgical intervention to prevent one of the outcomes listed in this definition. Examples of such medical events include allergic bronchospasm requiring intensive treatment in an emergency room or at home, blood dyscrasias or convulsions that do not result in inpatient hospitalization, or the development of drug dependency or drug abuse.
- F. **Life-Threatening:** An adverse event or suspected adverse reaction is considered “life-threatening” if, in the view of either the investigator or sponsor, its occurrence places the patient or subject at immediate risk of death. It does not include an adverse event or suspected adverse reaction that, had it occurred in a more severe form, might have caused death.

6.8 Stopping Rules

The study will stop if any of the following occur:

1. The participant decides to withdraw from the study.
2. The participant experiences a Serious Adverse Event (SAE) that, in the opinion of the investigator, is possibly, probably or definitely related to the study drug utilizing the National Cancer Institute's CTCAE system as a guide.
3. The participant experiences a medical condition that, in the opinion of the investigator, continuation on the study drug would be detrimental.
4. At least two patient have either:
 - a. AST or ALT >500 U/L or
 - b. Lille score >0.85.

In the event of a SAE, the site will report this to the Mayo Clinic study team. If the SAE is attributable to study drug, the Mayo Clinic study team will report the event to the Institutional Review Board and the FDA.

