2.7 Discontinuation

Discontinuation of the F-652 will occur if a participant experiences a Serious Adverse Event or UPIRTSO AND, in the opinion of the investigator and study adjudicator, is related to the study drug. Patients will be discontinued if grade 3 or higher CTCAE develop that are determined to be possibly or likely attributable to study drug.

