Laboratory: Biochemical parameters that are monitored include CRP, liver biochemistry, creatinine, and electrolytes. The study will be **stopped** if two or more patients have **either** A. AST or ALT > 500 U/L **or** B. Lille score > 0.85. The study will also be stopped if more than one patient (that is, two or more) has an adverse event grade 3 or above on the CTCAE scale that is determined to be possibly or likely attributable to study drug as per the study adjudicator. A patient will be **WITHDRAWN** from the dosing phase if Lille scores at any time are > 0.45 (treatment failure).

We recognize that determination of whether worsening of liver biochemical tests is due to the alcoholic hepatitis or study drug induced liver injury (DILI) is very difficult. An AST or ALT increase >500 IU/L would be considered an indication that the patient might have DILI since AST and ALT are typically < 250 U/L in AH. Such an increase of > 500 IU/L would trigger prompt evaluation and consideration of discontinuation of the study drug. A Lille score > 0.85 and an increase in MELD score >10 would also warrant discontinuation of the study drug. Considering how difficult it is to distinguish potential DILI from worsening of the underlying liver disease, we have incorporated an external adjudication of all suspected DILI events. This external adjudication is in addition to the data safety monitoring board (DSMB) which will monitor the entire study. A renowned hepatologist, [name], who is an internationally renowned expert both in the field of alcoholic hepatitis and DILI, has kindly agreed to serve as the external adjudicator for this IL 22 study. He will be contacted on an as needed basis when there is question of symptom causality.

The following parameters will be recorded for the safety evaluation:

- Adverse events
- Vital signs (pulse, heart rate, respiration)
- Physical examinations
- Clinical chemistry, hematology, coagulation, and urinalysis
- ECGs
- Chest X-Ray

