6.9 Individual Stopping Rules

The following are criteria for subject discontinuation from the study:

1. Subject withdraws study consent.
2. Subject is found to be ineligible for the protocol as per the Inclusion/Exclusion criteria.
3. Subject experiences disease progression.
4. Lille scores at any time are >0.45 (treatment failure). Patient will be taken off study drug, however, we will request that they complete follow-up.
5. A subject that requires more than 2 investigation drug (F-652) dose reductions.
6. Failure of the subject to comply with protocol requirements.
7. Exhibition of unacceptable toxicity which would make it difficult or dangerous to comply with further protocol requirements such as study visits, blood draws, etc.
8. There are changes in medical status of the subject such that the Investigator believes that subject safety will be compromised or that it would be in the best interest of the subject to stop participation in the study.
9. Death of the subject.
10. Subjects with a test consistent with pregnancy such as a positive beta-hCG.
11. Subject is lost to follow-up.
12. Any complication that requires prolongation of the hospitalization or change in treatment and in the opinion of the investigator is related to the study drug.

The investigator will utilize the National Cancer Institute's CTCAE system as a guide when determining the need for an individual participant to stop the study.

7 Statistical Plan

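### Section 6.8 makes single-participant events stop the whole study, section 2.4 adds an efficacy condition to escalation that 1.6 and 4.3 lack, and the stated 18 participants is a base count rather than a ceiling

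*Combined protocol and SAP*

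**What the plan says.** **Stopping.** Section 6.8 opens with "The study will stop if any of the following occur". Its first three items each concern one person:

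- Item 1 reads: "The participant decides to withdraw from the study".
- Item 2 reads: "The participant experiences a Serious Adverse Event (SAE) that, in the opinion of the investigator, is possibly, probably or definitely related to the study drug".
- Item 3 reads: "The participant experiences a medical condition that, in the opinion of the investigator, continuation on the study drug would be detrimental".

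Item 4 is a true study-level rule: at least two patients with AST or ALT above 500 U/L or a Lille score above 0.85.

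Other sections act on the individual. Section 2.7 states: "Discontinuation of the F-652 will occur if a participant experiences a Serious Adverse Event or UPIRTSO", with relatedness judged by the investigator and the study adjudicator. Section 6.9 is introduced by "The following are criteria for subject discontinuation from the study". Its item 1 is withdrawal of consent, and its item 8 reads "There are changes in medical status of the subject such that the Investigator believes that subject safety will be compromised". Section 6.1 repeats the AST/ALT and Lille stop and adds: "The study will also be stopped if more than one patient (that is, two or more) has an adverse event grade 3 or above", where the event is attributable to study drug. That last rule does not appear in 6.8.

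**Escalation.** Section 2.4 lets the 30 and 45 µg/kg cohorts start only if both safety and efficacy signals are seen. Section 1.6 relies on DLT counts, completed follow-up and available PK/PD data. Section 4.3 relies on safety and applies the same scheme to later steps.

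**Size.** The Summary gives 18 as the upper limit. Section 1.8 builds it as 9 + 9 and calls it the target number to complete. Section 1.6 adds 3 patients at a level where 1 of 3 has a DLT, and 6 patients at the MTD if only 1 of 3 responds.

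**The concern.** Finding the MTD is part of the primary objective (section 2), so the rules that stop, hold or extend the escalation are the design. A site reading 6.8 literally would have to treat one withdrawal as the end of the study. It would also miss the two-patient grade 3+ stop, which is found only in 6.1. Section 1.7 forbids departures from the protocol without prior IRB approval, except for an immediate hazard, and the DSMB meets every six months (10.2). Between meetings about six sites would apply whatever the text says.

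Followed literally, 2.4 can hold back escalation from a safe dose that shows no efficacy signal. In a dose-finding study that is an ordinary reason to go higher. The enrolment figure matters because it is stated as a limit, while the protocol's own rules pass it on ordinary paths, including one with no DLT at all.

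**Working it through.** **1. Stopping rules side by side**

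| Event | 6.8 | Elsewhere |
|---|---|---|
| One withdrawal | study stops (item 1) | that subject leaves (6.9 item 1) |
| One detrimental condition | study stops (item 3) | that subject leaves (6.9 item 8) |
| One related SAE | study stops (item 2) | that participant's drug stops (2.7) |
| Two patients, attributable grade 3+ | absent | study stops (6.1) |

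Items 1 and 3 duplicate individual rules. Item 2 sets a different threshold from 6.1. The documents give no related-SAE rate in alcoholic hepatitis. As an illustration, take assumed per-patient rates *q* of 5%, 10% and 20% over 18 patients, and let the same event count under both rules.

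- One-patient trigger, 1 − (1 − q)^18: 0.60, 0.85, 0.98.
- Two-patient trigger, 1 − (1 − q)^18 − 18q(1 − q)^17: 0.23, 0.55, 0.90.

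**2. Reproducing 18**

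2 MELD groups × 3 doses × 3 patients = 18. This is the count with no DLT and no response expansion.

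**3. Maximum under section 1.6**

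- If the 6.1 stop takes precedence and every DLT is a 6.1 event, only one DLT can occur before the study stops. The maximum is 18 + 3 = 21, or 21 + 6 = 27 with the response group.
- If the 6.1 stop does not bind, all six levels can reach 6 patients: 6 × 6 = 36. Adding the response group gives 42. This is a loose bound, because the response trigger is worded for a level with 3 patients.

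**4. Chance of exceeding 18 from the 3+3 alone**

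DLT rates *r* are assumed, constant across doses and groups.

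- *6.1 stop binds, every DLT a 6.1 event.* A 19th patient is enrolled only if the first 18 have exactly one DLT: 18r(1 − r)^17.
  - r = 2%: 0.255
  - r = 5%: 0.376
  - r = 10%: 0.300
- *6.1 stop does not bind.* Exact enumeration of the 3+3 in both groups, with the second opened only if the first has a tolerated dose. The first figure has no top-up of the lower level after de-escalation; the second tops it up to six.
  - r = 2%: 0.286 and 0.294
  - r = 5%: 0.510 and 0.542
  - r = 10%: 0.588 and 0.658

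**5. The +6 response group with no DLT**

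Response rates *p* come from section 1.9: 50% anticipated, 15-20% untreated. These are AST/ALT rates, whereas the 1.6 response also counts triglycerides. The trigger, exactly 1 of 3, is 3p(1 − p)². Section 1.6 also deems the drug ineffective if fewer than 2 of the added 6 respond. If that decision comes after phase I and ends the study, total enrolment is 9 + 6 = 15. Otherwise it is 18 + 6 = 24.

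| p | Trigger | At least 2 of 6 respond | Reaches 24 |
|---|---|---|---|
| 0.50 | 0.375 | 0.891 | 0.33 |
| 0.20 | 0.384 | 0.345 | 0.13 |
| 0.15 | 0.325 | 0.224 | 0.07 |

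**The case against.** Several stronger readings are tempting, and the documents do not support them.

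- *That all three single-participant items in 6.8 are slips.* This is safe for items 1 and 3 only. Section 1.5 says any related SAE will count as unexpected, and the primary endpoint in 2.3 is absence of unexpected SAEs. One related SAE is therefore a primary-endpoint failure, and a study-level halt could be deliberate. Stopping that participant's drug under 2.7 is compatible with also halting the study. Moving item 2 to the individual rules without asking could loosen an intended safeguard.
- *That the 6.1 stop contradicts the 3+3.* Section 1.6 de-escalates after 2 DLTs in 6, while 6.1 stops the study after two attributable grade 3+ events. An unconditional study stop naturally ends escalation, and a stop stricter than the 3+3 is a permissible choice. The extent of overlap is unknown because DLT is not defined. Precedence needs clarifying, but it is not an inconsistency.
- *That 2.4 blocks escalation with a calculable probability.* Sections 2, 2.3 and 5.1 give efficacy signals a wider meaning than a 30% AST/ALT fall: MELD, Lille, triglycerides, CRP and SAA. Section 1.6 already requires PK/PD data, so a reading of 2.4 as pharmacodynamic activity narrows the gap. The difference in wording stands, but no number can be attached to it.
- *That the response trigger means 24 patients.* A failed expansion may end the study at 15.

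It is also fair that 1.8 calls 18 a completion target. The conflict is with the Summary, which states a limit. Section 10.2 mentions a DSMB charter that is not among the documents and might settle some of this.

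**Conclusion.** The point holds in three parts. Section 6.8 misplaces two individual rules, sets a one-SAE study stop that is not reconciled with 2.7 and 6.1, and leaves out the two-patient grade 3+ stop. Section 2.4 puts an efficacy condition on escalation that 1.6 and 4.3 do not have. The Summary's 18 is a base count: the 3+3 can take it to 21 or to 36, depending on whether the 6.1 stop binds.

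The chance of passing 18 through the 3+3 is roughly a quarter to two thirds over assumed DLT rates of 2% to 10%. With no DLT, the response group alone takes enrolment to 24 with probability about 0.33 at the anticipated 50% response, if a failed expansion ends the study after phase I.

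The maxima follow from the protocol's rules under the stated precedence and overlap conditions. The 3+3 probabilities rest on assumed DLT rates. The maxima of 21 and 27, and the lower set of probabilities, further assume that every DLT is a 6.1 event. The textual conflicts need no assumption. This should be fixed; much of it is drafting, and it does not invalidate the design.

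**What to change.** 1. Move 6.8 items 1 and 3 to 6.9, where items 1 and 8 already cover them. Keep 6.8 for study-level criteria and add the two-patient attributable grade 3+ rule from 6.1.
2. Have the sponsor state what one related SAE does: halt the study (for example, a pause for adjudicator and DSMB review) or only stop that participant's dosing. Align 2.7, 6.1 and 6.8 with the answer.
3. Remove the efficacy condition from cohort escalation in 2.4. Keep it for the response expansion and the third dose.
4. Define DLT and say whether the 6.1 stop takes precedence over the 3+3. In the Summary and 1.8, give 18 as the base count, with the maximum under that one rule set: 21 (27 with the response group) if the stop takes precedence and every DLT is a 6.1 event, or 36 (about 42 as a loose bound) if it does not bind.

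The cost is amendment wording and a restated enrolment number. There are no new procedures, and patients beyond 18 arise only where 1.6 already provides for them. One consequence should be stated openly: if the 6.1 stop takes precedence and every DLT is a 6.1 event, the de-escalation step after 2 DLTs in 6 can never operate.

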6.9 Individual Stopping Rules

The following are criteria for subject discontinuation from the study:

1. Subject withdraws study consent.
2. Subject is found to be ineligible for the protocol as per the Inclusion/Exclusion criteria.
3. Subject experiences disease progression.
4. Lille scores at any time are >0.45 (treatment failure). Patient will be taken off study drug, however, we will request that they complete follow-up.
5. A subject that requires more than 2 investigation drug (F-652) dose reductions.
6. Failure of the subject to comply with protocol requirements.
7. Exhibition of unacceptable toxicity which would make it difficult or dangerous to comply with further protocol requirements such as study visits, blood draws, etc.
8. There are changes in medical status of the subject such that the Investigator believes that subject safety will be compromised or that it would be in the best interest of the subject to stop participation in the study.
9. Death of the subject.
10. Subjects with a test consistent with pregnancy such as a positive beta-hCG.
11. Subject is lost to follow-up.
12. Any complication that requires prolongation of the hospitalization or change in treatment and in the opinion of the investigator is related to the study drug.

The investigator will utilize the National Cancer Institute's CTCAE system as a guide when determining the need for an individual participant to stop the study.

7 Statistical Plan

7.1 Statistical Methods

Primary endpoint (safety): The number and percentage of patients with SAE and increase in MELD score > 5 up to Day 56 following administration of first dose of study drug will be summarized by each dose level. Ninety-five percent confidence interval of the percentage will be calculated too.

Summary of adverse event will also be provided by each dose level.

Secondary endpoint: Pharmacokinetics (PK) and pharmacodynamics (PD) of F-652 in patients with alcoholic hepatitis at the first dose level (10ug/kg) and subsequent dose levels will be determined by the study sponsor using standard pharmacological tools. The total exposure (area under the curve), maximum serum concentration, time at maximum concentration, last measurable serum concentration, time at last measurable concentration, clearance, volume of distribution, elimination half-life, accumulation ratio and dose proportionality will be calculated.

Efficacy signal endpoint: The main efficacy end point is the reduction of AST/ALT or serum triglycerides. If patients show a reduction of AST/ALT or serum triglyceride by 30% at day 42, the drug shows efficacy in this patient. We will calculate the percentage of patients with efficacy (rate) and its 95% confidence interval for each dose level.

We will also use the proportion of patients with 30% change of AST, ALT from baseline to Day 3, Day7, Day14, Day 28, Day 42 and Day 56 as the dependent variable, dose level and baseline AST, ALT and other patients' characteristic at baseline as the covariates to evaluate the change (efficacy) or drug by dose level. A random intercept will be included for accommodating the correlation among the repeated measurement.

Other efficacy endpoints: Paired t-test or signed-rank test will be used to compare the level Lille score. Linear mixed-effect models will be used to analyze the MELD score, triglycerides, CRP, and SAA1 in a similar way to the AST/ALT.

